#### 94 *Interventions*

95

96 Patients will be allocated in a 1:1 ratio to either the experimental or control group. In the  
97 former, fractures will be immobilized without reduction. In the latter, fractures will be reduced  
98 and immobilized. Provided instability, K-wires will be used. Instability is considered when, after  
99 reduction, alignment is lost: a new displacement or angulation larger than 50% and 10 degrees,  
100 respectively. General anesthesia will be mandatory exclusively for the control group. Discharge  
101 within two hours is the standard practice for both procedures. Plain radiographs will be  
102 obtained immediately after the intervention, at two weeks, three-, and nine-months during  
103 follow-up. Casts and K-wires will be removed at 6 weeks.

104

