#### 105 *Endpoints and follow up*

106

107 Children will be evaluated at about two and six weeks, three, six, and nine months after  
108 randomization. The primary endpoint is the upper extremity function assessed with the

109 PROMIS Pediatric Physical Function v2.0 at six months. Parents will serve as proxies of children  
110 <8 years with the proper format of the scale. From 8 years of age onwards, children will  
111 personally answer the questionnaire.

112  
113 The secondary outcomes are the ROM, ulnar variance, and fracture alignment in the sagittal  
114 and coronal planes. Plain radiographs of the wrist at two weeks, three and nine months and a  
115 standard goniometer will be used. Additionally, general anesthesia-related adverse effects,  
116 pressure ulcers according to the National Pressure Ulcer Advisory Panel, the number of days of  
117 required oral analgesics and Dahl classification of pin tract infections will also be registered[13].  
118 Further treatments such as radius osteotomy due to deformity, pseudoarthrosis cure, and  
119 remanipulation will also be recorded. Figure 1 depicts the flow of the study.

120

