#### 121 *Power analysis and sample calculation*

122

123 In a personal communication, [name] provided PROMIS range scores (36 to 39), variability  
124 (SD=10) and the minimally clinical important difference (MCID; 3 to 5) in children who have  
125 sustained an upper extremity fracture[14]. Therefore, assuming a non-inferiority threshold of 5,  
126 the trial requires a sample of 126 children (63 per group) to demonstrate no meaningful  
127 difference in the primary outcome (one-tailed  $\alpha=0.05$ ,  $\beta=0.2$ ). The sample will be inflated to  
128 152 (20%) due to the anticipation of loss to follow-up.

129

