#### 130 *Data management*

131

132 Participant's information will be recorded in the REDCap software. Registries will be password-  
133 protected with access granted just to the principal researcher and the study conductor. Data  
134 will be kept at the Instituto Roosevelt Medical Research Department. After completing the  
135 study, data will be preserved for two years, then all non-anonymized documents will be  
136 discarded.

137

138 *Statistical analysis*

139

140 Customary descriptive statistics will be used whether the variables are continuous or  
141 categorical. The intention-to-treat principle will be followed in this trial. Authors of the scale in  
142 the Northwestern University will standardize PROMIS scores once data gathering is completed,  
143 afterwards, the primary outcome will be evaluated with a t-test. The non-inferiority threshold  
144 will be compared to the lower bound of the 95% confidence interval of the mean difference.  
145 Secondary outcomes measured with continuous variables (i.e., ROM, ulnar variance, fracture  
146 alignment and number of days with oral analgesia) will be compared with the t-test or Mann-  
147 Whitney's U conforming to the distribution of the variables. Categorical outcomes will be  
148 compared with the Fisher's exact test (i.e., anesthesia-related adverse effects, pressure ulcers,  
149 pin tract infections, radius osteotomies, pseudoarthrosis, and remanipulations). Early  
150 termination of the trial is unlikely; therefore, interim analyses are not considered: given the  
151 proposed design, neither superiority nor futility of the experimental treatment is expected.

152

153 *Schedule*

154

155 Recruitment commenced in June 2021. The principal researcher personally interviews parents  
156 and children and the trial's general characteristics are completely explained. Benefits, such as a  
157 close follow-up (e.g., radiographs, pain, functionality) are also explained. Authors expect an  
158 average of ten patients monthly, therefore, recruitment and analysis should be complete by  
159 June 2023.

160 O?

161 *Declarations*

162

163 Both, Instituto Roosevelt and Pontificia Universidad Javeriana Ethics Committees, evaluated  
164 and accepted trial's protocol, research manual, consent and assent forms, and information  
165 brochures (approval No. 2021012101-002 and FM-CIE-0416-21, respectively). The datasets used  

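### Does the target of 152 children fall short because 126 was multiplied by 1.20 rather than divided by 0.80?

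*Combined protocol and SAP*

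**What the plan says.** All that the documents say about planning for attrition stands at the end of the section *Power analysis and sample calculation*. The base figure comes first: "the trial requires a sample of 126 children (63 per group) to demonstrate no meaningful" difference in the primary outcome, with a one-tailed alpha of 0.05 and beta of 0.2. The inputs are "assuming a non-inferiority threshold of 5" and a standard deviation of 10. The next sentence reads "The sample will be inflated to" followed by "152 (20%) due to the anticipation of loss to follow-up".

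No inflation formula is given, and no expected loss rate appears anywhere else. The primary outcome is the "PROMIS Pediatric Physical Function v2.0 at six months", so the loss that matters is loss before the six-month score. The *Statistical analysis* section compares the groups with a t-test and says that the threshold "will be compared to the lower bound of the 95% confidence interval of the mean difference".

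**The concern.** The 20% stands in the same sentence as the reason for the inflation, loss to follow-up, so it is easy to read as the expected loss. To keep N evaluable children after a loss fraction L, the target must be N/(1 − L), and multiplying by (1 + L) falls short. The printed 152 matches the multiplication, which looks like that familiar slip. On this reading a 20% loss would leave the trial below its own requirement of 126.

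At stake would be a primary analysis with slightly less power than planned, and a stated allowance that observed attrition could not be judged against.

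**Working it through.** **Inputs**

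- Required evaluable sample: 126, 63 per group (*Power analysis and sample calculation*).
- Inflated target: 152, labelled 20% (same section).
- Margin 5, SD 10, one-tailed alpha 0.05, power 80% (same section).
- Equal allocation: "Patients will be allocated in a 1:1 ratio" (*Interventions*).
- True difference d: not stated. It is assumed to be 0, with 1 and 2 points against the experimental arm as a range.

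**Reproducing 152**

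- As an increase of 20%: 126 × 1.20 = 151.2, rounded up to 152. Per group: 63 × 1.20 = 75.6, rounded up to 76, and 2 × 76 = 152. This matches.
- As cover for a 20% loss: 126/0.80 = 157.5, rounded up to 158. Per group: 63/0.80 = 78.75, rounded up to 79, and 2 × 79 = 158. This does not match.

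**Loss that 152 can absorb**

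- 152 − 126 = 26 children, and 26/152 = 17.1%.
- At 20% loss: 152 × 0.80 = 121.6 remain, a shortfall of 126 − 121.6 = 4.4 children.

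**What a 20% loss would cost in power**

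Normal approximation: power = Φ[(5 − d)/(10 × √(2/n)) − z], with n per group and 61 per group (122 in all) standing for the 121.6 above.

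For d = 0 and one-tailed 0.05 (z = 1.645):

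- n = 63: Φ(2.806 − 1.645) = 87.7% (87.4% with the t distribution).
- n = 61: Φ(2.761 − 1.645) = 86.8% (86.5% with the t distribution).

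For d = 0 and one-sided 0.025 (z = 1.960), which applies if the 95% interval in *Statistical analysis* is read as two-sided:

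- n = 63: Φ(2.806 − 1.960) = 80.1% (79.5% with the t distribution).
- n = 61: Φ(2.761 − 1.960) = 78.8% (78.2% with the t distribution).

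Over the range of assumed true differences (normal approximation):

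| d | alpha (one-sided) | 63 per group | 61 per group | difference (points) |
|---|---|---|---|---|
| 0 | 0.05 | 87.7% | 86.8% | 0.9 |
| 1 | 0.05 | 72.6% | 71.4% | 1.2 |
| 2 | 0.05 | 51.6% | 50.5% | 1.1 |
| 0 | 0.025 | 80.1% | 78.8% | 1.3 |
| 1 | 0.025 | 61.2% | 59.8% | 1.4 |
| 2 | 0.025 | 39.1% | 38.1% | 1.0 |

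The loss of two children per group costs 0.9 to 1.4 points throughout. The assumed true difference moves power far more than the inflation rule does.

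**Slack on the stated parameters**

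At one-tailed 0.05 and d = 0, the number per group for 80% power is 2 × [10 × (1.645 + 0.842)/5]² ≈ 49.5, so 50, or 51 with the t distribution. Two groups of 51 make 102, and 152 could then lose 50/152 = 32.9% and still reach 80%.

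**The case for a change.** The strongest case for a change runs as follows. A reader who sees 20% beside loss to follow-up will probably take it as the covered loss, and 152 does not cover 20% on any reading. A trial that lost 19% would look within plan, yet 152 × 0.81 = 123.1, so about 123 children would remain. The plan names no method for missing six-month scores, so under the t-test as written each missing score reduces the analysed number. If the 95% interval is two-sided, 126 has almost no slack. The remedy would be a single sentence.

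Part of this stands. The expected loss is not written down, and the sentence could be clearer. The rest carries less weight:

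- The shortfall exists only if 20% is the expected loss. The text does not say so, and that reading does not reproduce 152. If 20% is the size of the increase, comparing it with the tolerable loss shows no discrepancy.
- Attrition can be judged against the plan. Both 126 and 152 are printed, so the allowance of 26 children follows by subtraction.
- Power below 80% depends on taking the interval as two-sided, which the plan does not say. Even then the t-based figure is 79.5% at the full 63 per group, so the inflation is not its cause. How the stated alpha relates to the interval is a separate question about the base figure of 126.

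**Conclusion.** The concern does not call for a change. The figure 152 is a correct 20% increase on 126. It keeps 126 evaluable children up to a loss of 17.1%, and the only gap is that no expected loss rate is stated, a reporting detail that a reader can fill from the two totals.

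If 20% was in fact meant as the expected loss, the target is 6 children below 158, or 4 to 5 evaluable children below 126. That costs 0.9 to 1.4 points of power, for assumed true differences of 0 to 2 points and under either reading of alpha. At the stated one-tailed alpha of 0.05 and a true difference of 0, power stays near 87%.

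Rewording the sentence would leave the margin, the analysis, the decision rule and the number enrolled as they are. Enrolling 158 would add children for about one point of power. These results take 126 as the plan's requirement, with margin 5, SD 10 and equal loss in the two groups.

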#### 130 *Data management*

131

132 Participant's information will be recorded in the REDCap software. Registries will be password-  
133 protected with access granted just to the principal researcher and the study conductor. Data  
134 will be kept at the Instituto Roosevelt Medical Research Department. After completing the  
135 study, data will be preserved for two years, then all non-anonymized documents will be  
136 discarded.

137

138 *Statistical analysis*

139

140 Customary descriptive statistics will be used whether the variables are continuous or  
141 categorical. The intention-to-treat principle will be followed in this trial. Authors of the scale in  
142 the Northwestern University will standardize PROMIS scores once data gathering is completed,  
143 afterwards, the primary outcome will be evaluated with a t-test. The non-inferiority threshold  
144 will be compared to the lower bound of the 95% confidence interval of the mean difference.  
145 Secondary outcomes measured with continuous variables (i.e., ROM, ulnar variance, fracture  
146 alignment and number of days with oral analgesia) will be compared with the t-test or Mann-  
147 Whitney's U conforming to the distribution of the variables. Categorical outcomes will be  
148 compared with the Fisher's exact test (i.e., anesthesia-related adverse effects, pressure ulcers,  
149 pin tract infections, radius osteotomies, pseudoarthrosis, and remanipulations). Early  
150 termination of the trial is unlikely; therefore, interim analyses are not considered: given the  
151 proposed design, neither superiority nor futility of the experimental treatment is expected.

152

153 *Schedule*

154

155 Recruitment commenced in June 2021. The principal researcher personally interviews parents  
156 and children and the trial's general characteristics are completely explained. Benefits, such as a  
157 close follow-up (e.g., radiographs, pain, functionality) are also explained. Authors expect an  
158 average of ten patients monthly, therefore, recruitment and analysis should be complete by  
159 June 2023.

160 O?

161 *Declarations*

162

163 Both, Instituto Roosevelt and Pontificia Universidad Javeriana Ethics Committees, evaluated  
164 and accepted trial's protocol, research manual, consent and assent forms, and information  
165 brochures (approval No. 2021012101-002 and FM-CIE-0416-21, respectively). The datasets used  
166 and/or analyzed during the current trial will be available from the corresponding author upon  
167 reasonable request. Authors declare no competing interests. No funding to declare.

168 Acknowledgments: None. Authors' contributions: [name]: conception and design, data  
169 acquisition, analysis and interpretation, drafting of the manuscript and approval of the final  
170 version. [name]: critically revised the manuscript, drafting of the manuscript and approval of the  
171 final version

172

173 **Discussion**

174

175 This is the protocol of the first randomized trial that intends to compare functional outcomes of  
176 non-reduced versus reduced distal radius fractures in children. To authors knowledge, medical  
177 literature lacks experimental designs that take into account shortening and angulation in this  
178 age group.

179

180 The principal strength of this trial is the objective evaluation of functional outcomes with a  
181 scale constructed with modern measurement theory which is appropriate for the pediatric  
182 population, including previously healthy children who sustained a fracture of the wrist. In  
183 addition to functional recovery, anatomical parameters, as well as complications due to  
184 treatment will also be recorded.

185

186 The limitations of this trial are the lack of blindness for obvious reasons, and generalizability.  
187 Children will be recruited and treated in a specialized center. In most of authors' country  
188 institutions that deal with fractures in children a pediatric orthopedic surgeon is not available.  
189 The allocation will be open-labeled for patients, parents, and medical staff, this scenario may  
190 affect participants' feelings of well-being. However, results analyses will be blinded.

191

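### No masked outcome reading is planned, although the 3- and 9-month radiographs could be measured masked at small cost

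*Combined protocol and SAP*

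**What the plan says.** The Discussion names lack of blinding as a limitation and treats the reasons as self-evident. It continues: "The allocation will be open-labeled for patients, parents, and medical staff, this scenario may" affect how participants feel. The next sentence is the only safeguard offered: "However, results analyses will be blinded". The Statistical analysis section does not mention blinding, and no section describes coded arms, a masked extract or a point of unblinding.

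Endpoints and follow up lists ulnar variance and sagittal and coronal alignment as secondary outcomes, taken from wrist films at two weeks, three months and nine months. It names no reader and says nothing on masking. Under Interventions: "Casts and K-wires will be removed at 6 weeks".

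On roles, the contributions statement under Declarations credits one author with design, data "acquisition, analysis and interpretation, drafting of the manuscript and approval of the final" version. The other author "critically revised the manuscript, drafting of the manuscript and approval of the" final version, with no analysis role listed. Under Data management, records are "protected with access granted just to the principal researcher and the study conductor".

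**The concern.** Alignment and ulnar variance are measurements on an image. If the person measuring knows the arm, expectation can shift the reading in either direction. These outcomes matter here because the trial asks whether leaving a fracture unreduced is acceptable, and they are the anatomical evidence set beside the functional result.

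The Discussion gives one general reason for the lack of blinding and does not separate outcomes for which masking is impracticable from those for which it is not. A reader who meets the sentence on blinded analyses may also credit the trial with masked measurement, which it does not claim.

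A smaller issue is that blinded analysis is promised without a described mechanism, while the one author credited with analysis is also credited with acquiring the data.

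**Working it through.** No figure in the plan is in dispute, so the check sets the sections side by side.

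**1. What the promise covers.** The Discussion sentence concerns analyses. Outcome measurement is a separate step, and no section provides masking for it.

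**2. Which outcomes could be masked.**

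| Outcome | How it arises | Can it be masked under the present schedule? |
|---|---|---|
| PROMIS at six months (primary) | Answered by the child, or by a parent for children under 8; both know the allocation | No |
| Range of motion | Goniometer, in person | Not without changing the visit |
| Two-week film | Cast on; any K-wires in place; reduction just done or not done | No |
| Three-month film | Cast and wires out since 6 weeks | Yes, imperfectly |
| Nine-month film | Cast and wires out since 6 weeks | Yes |

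The three-month entry is imperfect because the experimental arm enters with 10 to 20 degrees of angulation left unreduced, while the control arm is reduced. The Background cites observational work in which fractures immobilized in situ regained alignment at about a year. Residual angulation may therefore still suggest the arm at three months, and should do so less at nine.

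**3. How much is affected.** There are three radiographic measures (sagittal alignment, coronal alignment, ulnar variance) at three dates.
- Readings per child: 3 × 3 = 9.
- Readings that can be masked: 3 × 2 = 6, and 6/9 is two thirds.
- Workload at the full 152 children: 152 × 2 = 304 examinations and 304 × 3 = 912 measurements.
- Workload if only the 126 required by the sample-size calculation are followed: 126 × 2 = 252 examinations and 252 × 3 = 756 measurements.

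**4. The analysis step.** The Medical Research Department randomizes centrally (Randomization) and is where the data are kept (Data management). It could therefore release a file with arms labeled A and B without any new body being created. Labels alone would not be enough:
- Interventions reserves general anesthesia for the control group and describes K-wires only there, so anesthesia effects, K-wire use and pin tract infections point to the arm.
- Immediate and two-week alignment probably do so too, because one arm is reduced and the other is not.

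The file is useful because the Statistical analysis section leaves each continuous secondary outcome to a t-test or a Mann-Whitney test according to its distribution. That choice can be settled before the code is opened.

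**5. Size of the bias.** The documents give no reader error, no standard deviation for alignment or ulnar variance, and no margin for either. Neither the amount nor the direction of a reader effect can be calculated from them.

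**The case against.** The strongest reply is that the primary conclusion is barely touched. PROMIS is reported by the child or parent. The scale's authors at "the Northwestern University will standardize PROMIS scores once data gathering is completed", and a named t-test with a stated confidence-bound rule follows. The main open-label bias lies in participant reporting; the Discussion already acknowledges it, and masked films do nothing about it. All of this stands, and it is why the point is an inexpensive improvement to secondary outcomes and not a threat to the trial's main result.

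Two stronger readings are tempting, and the documents do not support them.

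- **A reader might infer that the promised blinded analysis is not delivered**, because the analyst has met the children. The Schedule says: "Recruitment commenced in June 2021. The principal researcher personally interviews parents" and children. But the contributions statement is a general authorship credit with names removed. It cannot be tied to the principal researcher or to whoever runs the t-test, and someone who acquired data can still analyze coded arms. The text shows an undescribed safeguard in some tension with the listed roles, not a failed one.
- **A reader might infer that the films are read by staff who know the arm, in breach of the promise.** The protocol says medical staff are open-label but not that they take the measurements; it is silent on the reader. Unmasked reading would not in any case breach a sentence about analyses.

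The objection that coded arms alone can be decoded from early alignment is also fair. The fix therefore withholds those fields as well.

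**Conclusion.** The point holds in a limited form. The protocol plans no masked outcome reading, yet masking is feasible for alignment and ulnar variance at two of the three radiographic dates, or six of the nine readings per child. This assumes that casts and wires come out as scheduled and that the stored films can be stripped of identifiers. The benefit is confined to secondary outcomes, and its size cannot be stated from the documents. Bias in PROMIS is not reduced. The missing description of how the analysis is blinded is a minor gap to be filled; it is not evidence that the safeguard fails.

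**What to change.** 1. Have the existing reader measure all 3- and 9-month films in one batch at the end, in random order, with identifiers and allocation removed. Use these readings, and not those made during care, for the secondary analyses of alignment and ulnar variance.
2. Restate the Discussion sentence so that it lists what is masked (analysis on coded arms; reading of the 3- and 9-month films) and what is not (PROMIS, goniometry, two-week films).
3. As a clarification in the Statistical analysis section, state that the Medical Research Department releases a file with coded arms. It withholds the anesthesia, K-wire and pin-tract fields and the immediate and two-week alignment until the choice of tests is fixed. Those fields are then released for their planned comparisons.

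**Cost.** One de-identified image set, one coded export, and re-measurement of about 250 to 300 film examinations at the end. No additional reader, visit or radiograph is needed, and the change can be made although recruitment has begun. **Downsides.** The study readings of these films are available only at the end, masking is imperfect where residual angulation at three months suggests the arm, and the participant-reported primary endpoint gains nothing.
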